### 7.6.3 Sensitivity Analysis

As a sensitivity analysis for the primary efficacy endpoint:

- For the Cox regression model of the primary efficacy endpoint, the proportional hazard assumption will be checked by means of a Cox regression including treatment and its time dependent covariate, i.e., treatment group\*log(time). Censored patients at time 0 will not be used in the model. In case of strong rejection of proportionality, ie, p-value < 0.05, then restricted mean survival estimates will be calculated at Days 4, 8, 15, and 31 and weighted log-rank tests (if applicable) will also be calculated in addition to the hazard ratios from the stratified Cox regression model.
- Time-to sustained withdrawal of oxygen supplementation between each dose of plitidepsin versus control arm will be compared on the FAS population.
- Time-to sustained withdrawal of oxygen supplementation between each dose of plitidepsin versus control arm will be compared using an unstratified logrank test and Cox regression model on the ITT population. The hazard ratios, 95% CIs, and 2-sided p-values for the comparison of each dose of plitidepsin versus control arm will be presented.
- If at least the 5% of the patients in any treatment group are mis-stratified then the time-to sustained withdrawal of oxygen supplementation between each dose of plitidepsin versus control arm will be compared using a stratified log-rank test and Cox regression model on the ITT population. The model will be adjusted for the randomisation stratification factors as they were collected in IRT, ie, Geographical Region (Europe vs. Rest of the World), Charlson Comorbidity index (0-1 vs. 2 or Greater) and Barthel index (≥90 versus <90) as collected in IRT. The hazard ratios, 95% CIs, and 2-sided p-values for the comparison of each dose of plitidepsin versus control arm will be presented.

Moreover, as a sensitivity analysis for the key secondary efficacy endpoint:

• Time-to sustained hospital discharge between each dose of plitidepsin versus control arm will be compared on the FAS population.

 Time-to sustained hospital discharge between each dose of plitidepsin versus control arm will be compared using an unstratified log-rank test and Cox regression model on the ITT population. The hazard ratios, 95% CIs, and 2-sided p-values for the comparison of each dose of plitidepsin versus control arm will be presented.

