# 3.7 Primary Efficacy Endpoint

#### Table 14.2.1.1.1 Time to Sustained Withdrawal of Oxygen Supplementation (Intent-To-Treat Population)

Variable	Plitidepsin 2.5mg (N=XXX)	Plitidepsin 1.5mg (N=XXX)	Control Arm (N=XXX)	
Patients who Reported Sustained Withdrawal of Oxygen				
Supplementation, n (%) Censored Patients, n (%)	xxx (xx.x) xxx (xx.x)	xxx (xx.x) xxx (xx.x)	xxx (xx.x) xxx (xx.x)	
Time-to Sustained Withdrawal of Oxygen Supplementation (days) 95%				
25th percentile	xx.x (xx.x, xx.x)	xx.x (xx.x, xx.x)	xx.x (xx.x, xx.x)	
Median	xx.x (xx.x, xx.x)	xx.x (xx.x, xx.x)	xx.x (xx.x, xx.x)	
75th percentile	xx.x (xx.x, xx.x)	xx.x (xx.x, xx.x)	xx.x (xx.x, xx.x)	
Mean (SE)	xx.x (xx.x)	xx.x (xx.x)	xx.x (xx.x)	
Stratified Log-Rank Test				
2-sided p-value [b]	X.XXX	X.XXX		
2-sided p-value adjusted for Multiplicity [b,c]	X.XXX	X.XXX		
Supportive Analysis - Stratified Cox Regression Model				
Hazard Ratio [d,e]	X.XXX	X.XXX		
95% CI for Hazard Ratio [d,e]	X.XXX - X.XXX	X.XXX - X.XXX		
2-sided p-value [d]	X.XXX	X.XXX		

N = number of patients in analysis set. % = percentages are calculated based on N as the denominator.

CI = Confidence interval; SE = Standard Error.

Notes: Sustained withdrawal of oxygen supplementation (in days) with no subsequent reutilisation during remaining study period is defined as the first day, from randomisation through completion of the study, on which a patient

i. satisfies categories 0 to 4 on the 11-point WHO Clinical Progression Scale, and

ii. has no subsequent reutilisation of oxygen supplementation (5 to 10 on the 11-point WHO Clinical Progression Scale)

[a] Calculated using the Kaplan-Meier estimator. CIs derived based on Brookmeyer-Crowley method and using a log log transformation.

[b] 2-sided p-values calculated using a stratified log-rank test, including the fixed effect of the treatment group and levels of the randomisation stratification factors, ie, geographical region (Europe vs. Rest of the World), Charlson Comorbidity Index (0-1 vs. >1) and pre-baseline Barthel index ( $\geq$ 90 versus <90) as derived using the eCRF data as covariates.

[c] Stratified log-rank test p-values adjusted for multiplicity using the Hochberg step-up procedure.

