[d] Hazard Ratio, 95% CI and 2-sided p-values calculated using a stratified Cox proportional-hazards regression model, including the fixed effect of the treatment group and levels of the randomisation stratification factors, ie, geographical region (Europe vs. Rest of the World), Charlson Comorbidity Index (0-1 vs. >1) and pre-baseline Barthel index ( $\geq$ 90 versus <90) as derived using the eCRF data as covariates. Hazard Ratio > 1 favours a Plitidepsin arm to be associated with a shorter time to sustained withdrawal of oxygen supplementation than Control Arm.

[e] Statistics calculated relative to Control Arm.

Reference: Listing 16.2.6.5

Programming notes (not part of the table):

• Table template TEF011A.

- The displayed xxx do not reflect actual decimal precision. Please follow Section 2.11 for rounding rules.
- If 25th percentile, median or 75th percentile is not reached, present as "NR".

 Table 14.2.1.1.2 Time to Sustained Withdrawal of Oxygen Supplementation - Proportional Hazard Assumption and Restricted Mean Survival (Intent-To-Treat Population)

Variable	Time Dependent	Plitidepsin 2.5mg	Plitidepsin 1.5mg	Control Arm
	Covariate	(N=XXX)	(N=XXX)	(N=XXX)
p-value [a]	x.xxxx			
Restricted Mean Survival at Day 4		X.XXX	X.XXX	X.XXX
Restricted Mean Survival at Day 8		X.XXX	X.XXX	X.XXX
Restricted Mean Survival at Day 15		X.XXX	X.XXX	X.XXX
Restricted Mean Survival at Day 31		X.XXX	X.XXX	X.XXX

N = number of patients in analysis set.

Notes: Sustained withdrawal of oxygen supplementation (in days) with no subsequent reutilisation during remaining study period is defined as the first day, from randomisation through completion of the study, on which a patient

i. satisfies categories 0 to 4 on the 11-point WHO Clinical Progression Scale, and

ii. has no subsequent reutilisation of oxygen supplementation (5 to 10 on the 11-point WHO Clinical Progression Scale)

[a] Time dependent covariate p-value calculated using a stratified Cox proportional-hazards regression model, including the fixed effect of the treatment group and its time dependent covariate, i.e., treatment group\*log(time). Censored patients at time 0 will not be used in the model.

Reference: Listing 16.2.6.5

Programming notes (not part of the table):

• Table template TEF011A.

• The displayed xxx do not reflect actual decimal precision. Please follow Section 2.11 for rounding rules.

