• If time dependent covariate p-value is <0.05 then restricted mean survival at Day 4, Day 8, Day 15 and Day 31 will be calculated. Otherwise, restricted mean survival at Day 4, Day 8, Day 15 and Day 31 will not be calculated and their rows will be removed from the table.

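### The fallback for non-proportional hazards reports per-arm restricted means with no difference, SE or CI, and its weighted log-rank tests have no shell row and no named weights

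*SAP*

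**What the plan says.** SAP Section 7.6.3 checks proportional hazards for the primary endpoint with a treatment-by-log(time) term. The trigger is "In case of strong rejection of proportionality, ie, p-value < 0.05". Once it is met, "restricted mean survival estimates will be calculated at Days 4, 8, 15, and 31 and weighted log-rank tests (if applicable) will also be calculated". These come "in addition to the hazard ratios from the stratified Cox regression model", so they replace nothing.

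In the TFL shells, Table 14.2.1.1.2 is the only output for this step. It has one p-value for the time-dependent covariate and four restricted-mean rows, the last labelled "Restricted Mean Survival at Day 31". Each row has a single number per arm. The programming note reads "If time dependent covariate p-value is <0.05 then restricted mean survival at Day 4, Day 8, Day 15 and Day 31 will be calculated"; otherwise those rows are removed. It does not mention a weighted test.

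Table 14.2.1.1.1, the primary table, is produced whatever the proportionality check shows. It holds the stratified log-rank p-values, raw and Hochberg-adjusted, and the stratified Cox hazard ratios with 95% CIs. It also gives, by arm, the Kaplan-Meier quartiles with CIs and the mean with its SE.

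**The concern.** The primary objective compares each plitidepsin dose with control. When hazards are not proportional, a single hazard ratio averages an effect that changes over time, and a restricted-mean difference is the natural alternative. The SAP supports the step with a methods paper on using restricted mean survival time to estimate a treatment effect when proportionality is in doubt (Section 10, reference 3). The shell stops short of that: it prints arm means but never the contrast or its precision.

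The weighted log-rank promise has a related weakness. No weight function is named, and the condition attached to the promise is not explained. Different weights stress early or late differences, so weights picked after the curves are known can favour one conclusion, and this is an open-label trial.

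**Working it through.** **Text against shells.**

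- Restricted means: promised in 7.6.3 at four days; printed in Table 14.2.1.1.2 for three arms. 4 × 3 = 12 numbers.
- SE or CI of a restricted mean: none.
- Dose-minus-control difference, its CI or a p-value: none.
- Weighted log-rank test: promised conditionally in 7.6.3. It has no row in Table 14.2.1.1.2, in the sensitivity shell (Table 14.2.1.1.3, ordinary log-rank and Cox results only) or in the addendum shells.
- Weight function: not named anywhere.

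**What remains for the primary endpoint itself.** The stratified log-rank test gives a p-value but no effect size. The Kaplan-Meier quartiles and means are per arm. Every between-arm estimate with an interval is a hazard ratio: stratified, unstratified, IRT-stratified, bootstrap, or on the extended endpoint definition.

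**The document's own standard elsewhere.** Table 14.2.3.18 (viral load) gives a difference from control with SE, 95% CI and p-value. Table 14.2.1.1.1 gives each mean with an SE. The fallback table does neither.

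**What the missing interval would add (illustration only).** Section 2.3 states a control median of 8 days and HR 1.4, giving 5.7 days on plitidepsin; 8/1.4 = 5.71 reproduces this. Assume exponential times and no censoring before τ = 31 days. With λ = ln 2/median:

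- Restricted mean = (1 − e^(−λτ))/λ. Control: 10.755 days. Plitidepsin: 8.052 days. Difference: 8.052 − 10.755 = −2.70 days.
- Variance of min(T, τ) = 2[1/λ² − e^(−λτ)(τ/λ + 1/λ²)] − mean². Control: 83.8. Plitidepsin: 56.0. Sum: 139.8.
- SE = √(139.8/n) with n per arm.
- n = 203 (planned): SE 0.83, 95% CI −4.33 to −1.08.
- n = 67 (assumed): SE 1.45, 95% CI −5.53 to 0.13.
- n = 58 (assumed): SE 1.55, 95% CI −5.75 to 0.34.

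The SAP does not give the final number of patients. Section 8 says only that recruitment stopped before 33% of events, so 58 to 67 per arm is an assumption. The shell would show the same expected pair, 8.052 and 10.755, in all three cases. This example has proportional hazards, so it shows why a bare pair of means is hard to read. It does not measure harm when hazards are not proportional.

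**The horizon.** Under Section 6.1, Day 31 is 31 − 1 = 30 days after Day 1. The visit window is ±3 days (Section 2.2), so the visit may fall 30 − 3 = 27 days after Day 1. Section 7.6.1 censors event-free patients at that visit date. Follow-up to a full 31 days in every arm is therefore not guaranteed.

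**The case against.** The strongest reply is that this is a conditional sensitivity table and that the trial's conclusion does not depend on it. Much of that stands.

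- A reader might infer that no usable dose-versus-control comparison is left once proportionality fails. The documents do not support this. The stratified log-rank test with Hochberg adjustment (Section 7.6.1) is the primary analysis, the Cox model is only supportive, and the log-rank test remains a valid test of equal distributions under non-proportional hazards, though it may lose power.
- Contrasts that do not rely on hazards exist on a closely related question. Table 14.2.3.6.1 gives differences in the percentage needing oxygen therapy on the same four days, with exact 95% CIs. These use the FAS and do not require sustained withdrawal, so they inform but do not replace a restricted-mean difference.
- The printed means can be subtracted by hand. The Kaplan-Meier means with SEs in Table 14.2.1.1.1 even allow a rough interval, but their truncation point may differ by arm.
- The weighted tests are promised only conditionally, the shells are described as a guideline, and the addendum allows further tables. The absent row is therefore a mismatch between text and shell. It does not show that the test was withdrawn.

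What the reply does not answer is that the fallback, followed as written, gives no treatment effect with its uncertainty, and that the weights are open.

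**Conclusion.** The point holds as a reporting gap in the fallback. If the proportionality check gives p<0.05, Table 14.2.1.1.2 yields 12 arm-level means and no inferential contrast. The weighted log-rank tests have neither a shell nor a weight function. For the primary endpoint itself, the hazard ratio is then the only estimated between-arm effect with a confidence interval.

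The primary test and the design figures do not change. The gap matters only if the trigger fires, and how often it would cannot be worked out from the documents. The conclusion rests on comparing the text with the shells and needs no assumed sample size. It is worth correcting because the correction is cheap and concerns the primary endpoint.

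**What to change.** In Table 14.2.1.1.2, add for each dose versus control the restricted-mean difference with 95% CI and 2-sided p-value. Name one main horizon: Day 31, or the latest time up to Day 31 that follow-up supports in all arms given the visit window. Keep the earlier days descriptive.

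Either add a weighted log-rank row with its weight function named before the test is run, or delete that promise from Section 7.6.3. The addendum dates database lock to 26 April 2023, so rows introduced after that should be labelled post hoc, as its other outputs are.

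The cost is a few table rows and standard code. No new data are needed.

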#### Table 14.2.1.1.3 Time to Sustained Withdrawal of Oxygen Supplementation - Sensitivity Analysis (Intent-To-Treat Population)

Variable	Plitidepsin 2.5mg (N=XXX)	Plitidepsin 1.5mg (N=XXX)	Control Arm (N=XXX)
Sensitivity Analysis 1 - Unstratified Log-Rank Test			
2-sided p-value [a]	X.XXX	X.XXX	
Sensitivity Analysis 2 - Unstratified Cox Regression Model			
Hazard Ratio [b,c]	X.XXX	X.XXX	
95% CI for Hazard Ratio [b,c]	X.XXX - X.XXX	X.XXX - X.XXX	
2-sided p-value [b]	X.XXX	X.XXX	
Sensitivity Analysis 3 - Stratified Log-Rank Test using the Investigator-			
Derived Values from IRT			
2-sided p-value [d]	X.XXX	x.xxx	
Sancitivity Analysis 4 Stratified Cox Pagrassion Model using the			
Investigator Derived Values from IPT			
Hazard Ratio [e c]	X XXX	X XXX	
05% CI for Hazard Patio [e c]	л.ллл У УУУ У УУУ	л.ллл У УУУ У УУУ	
2-sided n-value [e]	л.ллл — Х.ХХХ У УУУ	$\lambda . \lambda \lambda \lambda = \lambda . \lambda \lambda \lambda$	
	A.AAA	A.AAA	

N = number of patients in analysis set; CI = Confidence interval; IRT = Interactive Response Technology.

Notes: Sustained withdrawal of oxygen supplementation (in days) with no subsequent reutilisation during remaining study period is defined as the first day, from randomisation through completion of the study, on which a patient

i. satisfies categories 0 to 4 on the 11-point WHO Clinical Progression Scale, and

ii. has no subsequent reutilisation of oxygen supplementation (5 to 10 on the 11-point WHO Clinical Progression Scale)

[a] 2-sided p-values calculated using an unstratified log-rank test with the fixed effect of the treatment group.

[b] Hazard Ratio, 95% CI and 2-sided p-values calculated using an unstratified Cox proportional-hazards regression model with the fixed effect of the treatment group. Hazard Ratio > 1 favours a Plitidepsin arm to be associated with a shorter time to sustained withdrawal of oxygen supplementation than Control Arm.

[c] Statistics calculated relative to Control Arm.

[d] 2-sided p-values calculated using a stratified log-rank test, including the fixed effect of the treatment group and levels of the randomisation stratification factors, ie, geographical region (Europe vs. Rest of the World), Charlson Comorbidity Index (0-1 vs. >1) and pre-baseline Barthel index ( $\geq$ 90 versus <90) as collected in IRT as covariates.

[e] Hazard Ratio, 95% CI and 2-sided p-values calculated using a stratified Cox proportional-hazards regression model, including the fixed effect of the treatment group and levels of the randomisation stratification factors, ie, geographical region (Europe vs. Rest of the World), Charlson Comorbidity Index (0-1 vs. >1) and pre-baseline Barthel index ( $\geq$ 90 versus <90) as collected in IRT as covariates. Hazard Ratio > 1 favours a Plitidepsin arm to be associated with a shorter time to sustained withdrawal of oxygen supplementation than Control Arm. Reference: Listing 16.2.6.5

Programming notes (not part of the table):

• Table template TEF011A.

• Sensitivity Analysis 3 and 4 will be only presented if at least the 5% of the patients in any treatment group are mis-stratified.

• The displayed xxx do not reflect actual decimal precision. Please follow Section 2.11 for rounding rules.

# Table 14.2.1.1.5 Time to Sustained Withdrawal of Oxygen Supplementation - Adding Oxygen Supplementation Status Analysis (Intent-To-Treat Population)

Variable	Plitidepsin 2.5mg (N=XXX)	Plitidepsin 1.5mg (N=XXX)	Control Arm (N=XXX)
Supportive Analysis – Adding Oxygen Supplementation Status			
Patients who Reported Sustained Withdrawal of Oxygen			
Supplementation, n (%)	xxx (xx.x)	xxx (xx.x)	xxx (xx.x)
Censored Patients, n (%)	xxx (xx.x)	xxx (xx.x)	xxx (xx.x)
Time-to Sustained Withdrawal of Oxygen Supplementation (days)			
25th percentile	xx.x (xx.x. xx.x)	xx.x (xx.x. xx.x)	xx.x (xx.x. xx.x)
Median	xx.x (xx.x. xx.x)	xx.x (xx.x. xx.x)	xx.x (xx.x. xx.x)
75th percentile	xx.x (xx.x, xx.x)	xx.x (xx.x, xx.x)	xx.x (xx.x, xx.x)
Mean (SE)	xx.x (xx.x)	xx.x (xx.x)	xx.x (xx.x)
Stratified Log-Rank Test			
2-sided p-value [b]	X.XXX	X.XXX	
2-sided p-value adjusted for Multiplicity [b,c]	X.XXX	X.XXX	
Supportive Analysis - Stratified Cox Regression Model			
Hazard Ratio [d,e]	X.XXX	X.XXX	
95% CI for Hazard Ratio [d,e]	x.xxx - x.xxx	X.XXX - X.XXX	
2-sided p-value [d]	X.XXX	X.XXX	

N = number of patients in analysis set. % = percentages are calculated based on N as the denominator.

CI = Confidence interval; SE = Standard Error.

Notes: Sustained withdrawal of oxygen supplementation (in days) with no subsequent reutilisation during remaining study period is defined as the first day, from randomisation through completion of the study, on which a patient

i. satisfies categories 0 to 4 on the 11-point WHO Clinical Progression Scale or 'No supplemental oxygen needed' is recorded in the 'Vital Sign Oxygen status' form, and

ii. has no subsequent reutilisation of oxygen supplementation (5 to 10 on the 11-point WHO Clinical Progression Scale or any oxygen supplementation is recorded in the 'Vital Sign Oxygen status' form)

[a] Calculated using the Kaplan-Meier estimator. CIs derived based on Brookmeyer-Crowley method and using a log log transformation.

[b] 2-sided p-values calculated using a stratified log-rank test, including the fixed effect of the treatment group and levels of the randomisation stratification factors, ie, geographical region (Europe vs. Rest of the World), Charlson Comorbidity Index (0-1 vs. >1) and pre-baseline Barthel index ( $\geq$ 90 versus <90) as derived using the eCRF data as covariates.

[c] Stratified log-rank test p-values adjusted for multiplicity using the Hochberg step-up procedure.

[d] Hazard Ratio, 95% CI and 2-sided p-values calculated using a stratified Cox proportional-hazards regression model, including the fixed effect of the treatment group and levels of the randomisation stratification factors, ie, geographical region (Europe vs. Rest of the World), Charlson Comorbidity Index (0-1 vs. >1) and pre-baseline Barthel index ( $\geq$ 90 versus <90) as derived using the eCRF data as covariates. Hazard Ratio > 1 favours a Plitidepsin arm to be associated with a shorter time to sustained withdrawal of oxygen supplementation than Control Arm. [e] Statistics calculated relative to Control Arm.

#### Reference: Listing 16.2.6.11

- Table template TEF011A.
- The displayed xxx do not reflect actual decimal precision. Please follow Section 2.11 for rounding rules.
- If 25th percentile, median or 75th percentile is not reached, present as "NR".

Repeat the Table 14.2.1.1.1 for the below tables and use the footnotes.

#### Table 14.2.1.2 Time to Sustained Withdrawal of Oxygen Supplementation (Full Analysis Set)

N = number of patients in analysis set. % = percentages are calculated based on N as the denominator.

CI = Confidence interval; SE = Standard Error.

Notes: Sustained withdrawal of oxygen supplementation (in days) with no subsequent reutilisation during remaining study period is defined as the first day, from randomisation through completion of the study, on which a patient

- i. satisfies categories 0 to 4 on the 11-point WHO Clinical Progression Scale, and
- ii. has no subsequent reutilisation of oxygen supplementation (5 to 10 on the 11-point WHO Clinical Progression Scale)

[a] Calculated using the Kaplan-Meier estimator. CIs derived based on Brookmeyer-Crowley method and using a log log transformation.

[b] 2-sided p-values calculated using a stratified log-rank test, including the fixed effect of the treatment group and levels of the randomisation stratification factors, ie, geographical region (Europe vs. Rest of the World), Charlson Comorbidity Index (0-1 vs. >1) and pre-baseline Barthel index ( $\geq$ 90 versus <90) as derived using the eCRF data as covariates.

[c] Key secondary efficacy endpoints p-values adjusted for multiplicity using the Hochberg step-up procedure.

[d] Hazard Ratio, 95% CI and 2-sided p-values calculated using a Cox proportional-hazards regression model, including the fixed effect of the treatment group and levels of the randomisation stratification factors, ie, geographical region (Europe vs. Rest of the World), Charlson Comorbidity Index (0-1 vs. >1) and pre-baseline Barthel index (≥90 versus <90) as derived using the eCRF data as covariates. Hazard Ratio > 1 favours a Plitidepsin arm to be associated with a shorter time to sustained withdrawal of oxygen supplementation than Control Arm. [e] Statistics calculated relative to Control Arm.

Reference: Listing 16.2.6.5

Programming notes (not part of the table):

- Table template TEF011A.
- The displayed xxx do not reflect actual decimal precision. Please follow Section 2.11 for rounding rules.
- If 25th percentile, median or 75th percentile is not reached, present as "NR".

#### Table 14.2.1.3 Time to Sustained Withdrawal of Oxygen Supplementation (Per Protocol)

N = number of patients in analysis set. % = percentages are calculated based on N as the denominator.

CI = Confidence interval; SE = Standard Error.

Notes: Sustained withdrawal of oxygen supplementation (in days) with no subsequent reutilisation during remaining study period is defined as the first day, from randomisation through completion of the study, on which a patient

- i. satisfies categories 0 to 4 on the 11-point WHO Clinical Progression Scale, and
- ii. has no subsequent reutilisation of oxygen supplementation (5 to 10 on the 11-point WHO Clinical Progression Scale)

[a] Calculated using the Kaplan-Meier estimator. CIs derived based on Brookmeyer-Crowley method and using a log log transformation.

[b] 2-sided p-values calculated using a stratified log-rank test, including the fixed effect of the treatment group and levels of the randomisation stratification factors, ie, geographical region (Europe vs. Rest of the World), Charlson Comorbidity Index (0-1 vs. >1) and pre-baseline Barthel index ( $\geq$ 90 versus <90) as derived using the eCRF data as covariates.

[c] Key secondary efficacy endpoints p-values adjusted for multiplicity using the Hochberg step-up procedure.

[d] Hazard Ratio, 95% CI and 2-sided p-values calculated using a Cox proportional-hazards regression model, including the fixed effect of the treatment group and levels of the randomisation stratification factors, ie, geographical region (Europe vs. Rest of the World), Charlson Comorbidity Index (0-1 vs. >1) and pre-baseline Barthel index ( $\geq$ 90 versus <90) as derived using the eCRF data as covariates. Hazard Ratio > 1 favours a Plitidepsin arm to be associated with a shorter time to sustained withdrawal of oxygen supplementation than Control Arm.

[e] Statistics calculated relative to Control Arm.

Reference: Listing 16.2.6.5

- Table template TEF011A.
- The displayed xxx do not reflect actual decimal precision. Please follow Section 2.11 for rounding rules.
- If 25th percentile, median or 75th percentile is not reached, present as "NR".

